## IX. Flow chart for Prospective Study

### 3.2 Primary Study Endpoints

The primary endpoint is the mean time from admission to delivery.

Please note that the time the intervention (outpatient) group spends in the Family Birth Center the night before (for fetal heart rate monitoring, Foley placement, etc) will be added into the total time of inpatient admission

### 3.3 Secondary Study Endpoints

#### I. Baseline maternal data

##### A. Date of birth

- B. Race and ethnicity
- C. Pre pregnancy body mass index
- D. Gravidity
- E. Parity
- F. Medical comorbidities
- G. Surgical history
- H. Major complications during this pregnancy (i.e. gestational diabetes)
- II. Intervention (outpatient) group data
  - A. Method of Foley catheter insertion: digital or sterile speculum
  - B. Foley catheter expulsion at home: yes/no, time of expulsion
  - C. Return to the Family Birth Center earlier than scheduled and reason (labor, rupture of membranes, decreased fetal movement, vaginal bleeding, pain, fever, or other)
  - D. Bishop score before Foley placement
  - E. Bishop score on the morning of admission for continuation of the labor induction
  - F. First induction method used after admission in the morning
    - a. Oxytocin
    - b. Artificial rupture of membranes
    - c. Oxytocin + artificial rupture of membranes
    - d. If Foley catheter still in place, Foley + oxytocin
- III. Procedural data for both groups
  - A. Gestational age at delivery
  - B. Primary providing team in the Family Birth Center (Obstetrics, Midwifery, or Family Medicine)
  - C. Use of Foley catheter: yes/no, date and time
  - D. Use of pharmacologic cervical ripening: yes/no, date and time, number of doses
  - E. Use of oxytocin: yes/no, date and time, maximum dosage
  - F. Rupture of membranes: spontaneous or artificial, date and time
  - G. Epidural placement: yes/no, date and time
  - H. IV pain medication administration prior to delivery—time, medication, and dose
  - I. Date and time of delivery
  - J. Number who delivered within 12, 24, 36, 48 hours from initiation of cervical ripening
  - K. Number who delivered before midnight of the following day
  - L. Meconium passage prior to delivery: yes/no, thin or thick
  - M. Total number of cervical exams
  - N. Mode of delivery
    - 1. Normal spontaneous vaginal delivery
    - 2. Vacuum assisted vaginal delivery and indication
    - 3. Forceps assisted vaginal delivery and indication
    - 4. Cesarean delivery
  - O. If a cesarean delivery was performed:
    - 1. Indication for cesarean (non-reassuring fetal heart status, umbilical cord prolapse, uterine rupture, placental abruption, failed operative delivery, arrest of dilation, arrest of descent, and other)
    - 2. Type of cesarean—emergent, urgent, or non-urgent (“Alpha,” “Beta,” or “Charlie”)
    - 3. Cervical dilation at the time of cesarean, if known

4. Stage of labor at the time of cesarean

IV. Maternal outcomes

A. Intrapartum complications

1. Intrapartum fever
2. Chorioamnionitis
3. Suspected or confirmed placental abruption
4. Category II or category III fetal heart tracing requiring in utero resuscitation as documented in the electronic record during the cervical ripening phase only

B. Estimated blood loss at delivery

C. Postpartum hemorrhage: yes/no, if pharmacologic or surgical treatments required

D. Infection (endomyometritis, wound infection, or urinary tract infection within 30 days)

E. Readmission within 6 weeks of delivery and reason

F. Length of inpatient hospital stay (in hours from time of admission to noon on the day of discharge)

V. Fetal outcomes

A. Sex

B. Birth weight (grams)

C. Position at delivery (occiput anterior, occiput posterior, occiput transverse, or unknown)

D. APGAR scores at 1 and 5 minutes

E. Umbilical cord blood gas-pH and base excess

F. Disposition after delivery: level I, II, or III. If II or III, reason for admission.

G. Day of life on which discharge occurred

H. Neonatal death within 30 days and reason

VI. Maternal satisfaction data

A. Average scores for each question on the maternal satisfaction survey (see attached)

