  - 1. While the Foley catheter is in place, the patient can use the following non pharmacologic methods to decrease discomfort: warm baths, massage, frequent position changes in a comfortable environment, relaxation techniques, and gentle stretching
  - 2. Pharmacologic methods available to the patient include:
    - (a) Tylenol 1000mg orally q6 hours as needed for pain
    - (b) Morphine 10 mg IM once prior to dismissal
- K. The patient will be instructed to return to the Family Birth Center approximately 12 hours following their Foley bulb placement.
- L. The patient will be given verbal and written instructions as follows:

1. To return immediately to the Family Birth Center if she feels decreased fetal movement, if she is concerned her membranes ruptured, if she has vaginal bleeding more than spotting, if she has regular, painful contractions, if she has severe pain, if she develops a fever of  $\geq 100.4\text{F}$  or  $\geq 38.0\text{ C}$ , or if she develops any symptoms concerning to her.
2. If the Foley catheter is expelled at home, she is to record the time of expulsion. She does not need to return to the Family Birth Center earlier than planned due to expulsion.
3. She will be provided with the 24 hour direct access line for the Family Birth Center to call with any questions or concerns.

M. On arrival to the Family Birth Center at 12 hours later, the induction will be continued.

1. The providing team will decide to proceed with oxytocin and/or artificial rupture of membranes.
2. The oxytocin dose will be increased as determined by the Family Birth Center oxytocin low dose infusion regimen.
3. The patient will have continuous electronic fetal monitoring.
4. The remainder of her care during the first, second, and third stages of labor will be at the discretion of the providing team.
5. If the Foley is still in place when the patient arrives, a provider should gently tug on it. If it does not come out, the providing team may choose to deflate and remove the Foley catheter (and then proceed with artificial rupture of membranes or oxytocin) OR leave the Foley in situ and place vaginal misoprostol.

N. All patients' labor progress will be monitored using a partogram. Cesarean delivery will not be performed for arrest of labor or failed induction unless all criteria have been met as outlined by the Family Birth Center Workgroup protocol made effective 6/2/14.

V. Protocol for the control group (Randomized Control Trial)

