### 3.4 Primary Safety Endpoints

The primary safety outcomes are as follows: heavy vaginal bleeding, severe pain (return to hospital overnight for unrelieved pain), mode of delivery, intrapartum complications (as described above), and fetal outcomes (as described above). These will include overall fetal and maternal survival rates. Based on previous studies, we do not anticipate any difference between safety endpoints in the inpatient vs. outpatient groups.

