## **5.6 Prior and Concomitant Therapy**

Information about concomitant pharmacologic pain control therapies will be collected. Please see the “protocol for the intervention group” in the section 3.1 above for a description of pain control options for the outpatient group. As this section states, non pharmacologic options (warm baths, massage, frequent position changes, relaxation techniques, gentle stretching), Tylenol, and Morphine 10 mg IM once before discharge are permitted for the intervention group. The inpatient group will have the standard array of pain control options that will be left to provider discretion.

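### Endpoint III.H in section 3.3 counts only IV pain medication, so it leaves out the IM morphine that is the only opioid listed for outpatients during ripening

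*Combined protocol and SAP*

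**What the plan says.** Section 3.3 lists the secondary endpoints. Under "Procedural data for both groups", item III.H reads "IV pain medication administration prior to delivery—time, medication, and dose". Item III.G covers epidurals. No other item in section 3.3 names IM or oral analgesia.

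Section 3.1, part IV.J, gives outpatients two pharmacologic options while the catheter is in place: oral Tylenol as needed, and "Morphine 10 mg IM once prior to dismissal". Section 5.6 repeats the second: "Morphine 10 mg IM once before discharge are permitted for the intervention group". For the comparison group it says: "The inpatient group will have the standard array of pain control options that will be left to provider discretion". No routes are given for that group.

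Section 5.6 also states: "Information about concomitant pharmacologic pain control therapies will be collected". This carries no route limit, but it is not tied to any endpoint in section 3.3.

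Three other statements bear on the point:

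- The Study Summary says that secondary endpoints will be compared between groups.
- Section 3.1, part VII, says that the endpoints abstracted from the electronic record are those of section 3.3.
- The multiplicity paragraph of section 7.3 restricts evaluation to outcomes fixed in advance.

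**The concern.** III.H applies one route limit to two groups whose options differ. During ripening, the one opioid listed for an outpatient cannot count under III.H. An inpatient's opioid counts whenever it is given IV. The same need for relief can therefore be recorded in one group and not in the other.

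What is at stake is modest but real. The trial's severe-pain safety outcome in section 3.4 is defined by returning to hospital overnight for unrelieved pain. The related item in section 3.3, part II, "Return to the Family Birth Center earlier than scheduled and reason", is collected for outpatients only. A woman who never leaves hospital cannot have either event. Epidural use and III.H are thus among the few analgesia items recorded in both groups, and a reader of the results would naturally compare them.

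**Working it through.** The documents give no rate of analgesic use, so there is no planned figure to reproduce. The check is a comparison of wording, followed by an illustration under stated assumptions.

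**Wording**

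| Item | Source | Route |
|---|---|---|
| Systemic analgesia endpoint, both groups | 3.3, III.H | IV only |
| Opioid listed for outpatients in ripening | 3.1, IV.J; 5.6 | IM, once before dismissal |
| Inpatient analgesia | 5.6 | not stated |
| General data collection on pain drugs | 5.6 | no limit |

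The first two rows do not meet. The fourth shows that the IM data are meant to be collected. Nothing brings them into the planned comparison.

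**What is lost.** III.H runs until delivery. After an outpatient returns, her care is at the team's discretion (3.1, IV.M), and any IV drug given then is recorded. A count of women with any recorded drug therefore loses only those who have IM and never IV. The recorded times, drugs and doses lose every IM dose.

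**Illustration.** Let P be the true proportion receiving any parenteral pain medication before delivery, assumed equal in both groups. Let m be the share of those users who have IM only.

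- Recorded proportion in a group = P × (1 − m)
- Spurious difference, outpatient minus inpatient = P × (m_in − m_out)

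With P = 50% (assumed), 20 of 40 outpatients and 80 of 160 inpatients are true users. If m_out = 30% and m_in = 0, then 6 outpatients drop out of the count. The record shows 14/40 = 35% against 80/160 = 50%, a difference of -15 points. Varying both shares gives these spurious differences in percentage points:

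| IM-only share, outpatient users | inpatient 0% | inpatient 10% | inpatient 30% | inpatient 50% |
|---|---|---|---|---|
| 10% | -5 | 0 | +10 | +20 |
| 30% | -15 | -10 | 0 | +10 |
| 50% | -25 | -20 | -10 | 0 |

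The result scales with P. With no inpatient IM-only use, and P from 30% to 70%, it runs from 0.30 × 0.10 = 3 points to 0.70 × 0.50 = 35 points in the outpatients' favour. The sign depends only on which group has the larger IM-only share.

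**The case against.** The strongest reply has four parts.

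- **Section 5.6 already plans to collect the data.** It has no route limit and names the IM morphine in the same paragraph. This stands against any claim that the dose goes unrecorded. It does not repair III.H, which remains the item listed for comparison.
- **The direction of error is not shown.** A reader might infer that III.H is biased in favour of outpatient care. The documents do not support that as a certainty: inpatient routes are unstated, and an inpatient given only IM medication is missed in the same way. Outpatients who later receive IV drugs stay in the count. This part stands in full.
- **III.H is not called a pain outcome.** A reader might infer that the trial will make outpatient ripening look less painful than it is. The plan files III.H beside oxytocin and epidural use, and neither the secondary objectives nor the secondary hypotheses name pain or analgesic use. This also stands. The item is nevertheless headed a secondary endpoint, and such endpoints are to be compared.
- **A wider definition could bring its own bias.** Outpatients may take oral Tylenol at home, and section 9.3 says that all data are abstracted from the electronic record, which may not hold home doses. This stands and limits the fix.

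**Conclusion.** The point holds as a mismatch between III.H and sections 3.1 and 5.6. The between-group item, as worded, excludes the one opioid the protocol lists for outpatients during ripening. It can therefore understate outpatient opioid use relative to inpatients.

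The documents fix neither the size nor the net direction. The table in the working runs from -25 to +20 points at an assumed true use of 50% in both groups, with zero wherever the IM-only shares are equal. The negative values, which favour outpatients, are plausible if inpatient opioids are mainly IV, but that is an assumption. A p-value calculated with no inpatient IM-only use would rest on that assumption and should not be quoted alone.

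The matter is minor. It does not touch the primary endpoint, the sample size or any named hypothesis.

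**What to change.** Reword III.H along these lines: *parenteral (IV or IM) pain medication from the start of cervical ripening to delivery, including doses given at the placement visit before dismissal: time, medication, route and dose.* Record it identically in both groups, refer to it from section 5.6, and report IV and IM separately beneath the combined count.

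Leave oral drugs taken at home out of the between-group count, because the electronic record may not capture them. They can be described for the outpatient group alone where known.

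The cost is one line in section 3.3, a cross-reference in 5.6 and a route field on the case report form. IM doses given in the Family Birth Center should be in the electronic record already being abstracted, so women already enrolled can be completed from the same source. The change concerns measurement only and alters no treatment.

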**IV. Protocol for the intervention group (Both Randomized Control Trial and Prospective Study)**

- A. The patient will present to the Family Birth Center at 0730 or 1930.
- B. A nonstress test (NST) will be performed
  - 1. The fetal heart rate (FHR) is observed by external monitoring for at least 20 minutes. The FHR is observed for the presence of accelerations, at least 2 in 40 minutes that peak at least 15 beats per minute above the baseline and last for at least 15 seconds. The absence of at least 2 accelerations in up to 40 minutes is considered nonreactive.
  - 2. A nonreactive NST, the presence of  $\geq 3$  variable decelerations in a 20 minute period, late-appearing decelerations, or any deceleration lasting  $\geq 1$  minute should be considered criteria for exclusion.
- C. An ultrasound will be performed for fetal presentation and amniotic fluid index.
- D. A cervical exam will be performed with calculation of a Bishop score.
- E. The patient will be asked the following standard questions.
  - 1. Are you experiencing any of the following: regular, painful contractions? Decreased fetal movement? Vaginal bleeding? Leakage of fluid from the vagina concerning for rupture of membranes? Fevers or chills?
  - 2. She will be excluded from the trial based on her answers, as described in section 4.2 "Exclusion Criteria."
- F. A Foley catheter will be placed if the following criteria have been met: the nonstress test is reactive, the fetal presentation is cephalic, the amniotic fluid index is 5 centimeters or more, the Bishop score is  $<9$ , the cervical dilation is  $<3$  cm, and she has no other clinical characteristics that exclude her from the trial.
- G. An obstetric provider will place a 16 French Foley catheter through the internal os. The balloon will be inflated with 60cc of normal saline. The distal end of the Foley will be taped to the patient's inner thigh.
- H. The fetal heart rate tracing will be monitored for 1 hour after Foley placement.
- I. The patient will be sent home if the following criteria are met: the fetal heart rate tracing is reactive and category I; there is no evidence of rupture of membranes, spontaneous labor, or vaginal bleeding more than spotting; and maternal vital signs are within normal range.
- J. Pain control options

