## 7.2 Sample Size Determination for Prospective Study

A power analysis was performed and assumed a standard deviation of 8 hours. With 40 subjects in the Foley intervention arm and 160 subjects in the standard of care group, we would have 80% power to detect a  $\frac{1}{2}$  standard deviation reduction in the predelivery hospitalization time from 16 to 12 hours in the standard of care and intervention groups, respectively. This also assumes a 2-sided significance level of 0.05.

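### Time from start of ripening to delivery is pre-specified only as yes/no counts; adding it in hours, beside the hospital-hours primary endpoint, would give an estimate and recover power for moderate differences

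*Combined protocol and SAP*

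**What the plan says.** Section 3.2 states: "The primary endpoint is the mean time from admission to delivery". It adds that the outpatient group's earlier time in the unit "will be added into the total time of inpatient admission". Hours at home between dismissal and return are therefore left out, which agrees with the primary objective in 2.1 (length of pre-delivery hospitalization).

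Section 3.1 fixes the usual length of the home period. Under IV.H, "The fetal heart rate tracing will be monitored for 1 hour after Foley placement". Under IV.K, "The patient will be instructed to return to the Family Birth Center approximately 12 hours following their Foley bulb placement". Under IV.L.2, expulsion of the catheter at home does not by itself bring the return forward.

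Section 3.3 deals with the length of the process under procedural data. III.J is "Number who delivered within 12, 24, 36, 48 hours from initiation of cervical ripening", and III.K counts deliveries before midnight of the following day. The same list records the date and time of Foley use (III.C), of pharmacologic ripening (III.D) and of delivery (III.I) in both groups. Item IV.F of the list is total stay to discharge, which is a different quantity. Neither the secondary objectives (2.2) nor the secondary hypotheses (7.3) name the interval from start of ripening to delivery.

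**The concern.** A shorter hospital stay can arise because the process is no longer than before and part of it takes place at home, or because the process is longer and the extra hours are uncounted. Hospital hours alone do not separate the two. The quantity that does is the interval from start of ripening to delivery. The protocol treats it as relevant: section 1.1 reports total induction time from the cited outpatient-versus-inpatient Foley trial next to that trial's saving in inpatient time.

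In this plan the interval appears only after being cut at fixed hours. The counts give no estimate in hours to set beside a primary result in hours, and cutting a continuous time loses power. The plan could therefore report a significant saving in hospital hours with only a blunt statement about total time.

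**Working it through.** **1. The plan's own figure.** Section 7.2: 40 and 160 women, means 12 and 16 h, SD 8 h, two-sided 0.05.
- Standard error = 8 × √(1/40 + 1/160) = 1.414 h.
- Noncentrality = 4 / 1.414 = 2.83.
- Power from the noncentral t with 198 df = 80.4%; normal approximation 80.7%. The stated 80% is reproduced.

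**2. Hours not counted.** Return at about 12 h (IV.K) minus 1 h of monitoring in the unit (IV.H) = about 11 h at home, for a woman who goes home and returns as scheduled.

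**3. What a hospital-hours saving implies for total time.** Change in total time = home hours − saving, taking time in the unit before ripening starts as equal in the two groups.

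| Saving in hospital hours | Source | Change with 11 h at home |
|---|---|---|
| 4 h | 16 to 12 h, section 7.2 | (12 + 11) − 16 = +7 h |
| 9.6 h | cited Foley trial, section 7.1 | 11 − 9.6 = +1.4 h |
| 11.1 h | cited trial against prostaglandin gel, section 7.1 | 11 − 11.1 = −0.1 h |

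With 9 to 12 h at home, the first row runs from +5 to +8 h.

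**4. Power on the interval and on the counts.** The documents give no SD or mean for this interval. I assume normal times, a control mean of 16 h and SD 8 h, borrowed from section 7.2. The proportion delivered by c hours is Φ((c − mean)/SD). Power on the interval is from the noncentral t. Power on a count is from the two-proportion normal approximation, with the pooled variance under the null. Example for 4 h at the 24 h cut:
- Proportions: Φ(8/8) = 84.1% and Φ(4/8) = 69.1%; pooled 0.8 × 84.1% + 0.2 × 69.1% = 81.1%.
- Null standard error = √(0.811 × 0.189 × (1/160 + 1/40)) = 0.069; alternative standard error = √(0.841 × 0.159/160 + 0.691 × 0.309/40) = 0.079.
- Power = Φ((0.150 − 1.96 × 0.069)/0.079) = 57%.

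| Lengthening | Interval in hours | 24 h count | 12 h count | 36 h count |
|---|---|---|---|---|
| 3 h | 56% | 37% (84.1 vs 73.4% delivered) | 30% (30.9 vs 19.1%) | 16% |
| 4 h | 80% | 57% (84.1 vs 69.1%) | 47% (30.9 vs 15.9%) | 24% |
| 7 h | 99.8% | 96% (84.1 vs 55.0%) | 89% (30.9 vs 8.5%) | 54% |

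At 48 h nearly all women have delivered in every scenario, so that count carries almost no information.

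**5. Sensitivity to the assumed SD.** For 4 h, the interval, 24 h count and 12 h count have power 96%, 74% and 62% at SD 6; 61%, 43% and 35% at SD 10; 47%, 33% and 27% at SD 12. The ordering does not change. For 7 h, the 24 h count has 99.6% at SD 6 and 74% at SD 12 (69% with Fisher's exact test, by simulation).

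**The case against.** The strongest reply is that leaving out home hours is the purpose of the study. The objective is pre-delivery hospitalization, and section 3.2 counts the outpatient group's placement visit, so hospital time is treated fairly. This stands: the primary endpoint needs no change.

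The counts are also not without an analysis. The Study Summary assigns chi-square or Fisher's exact tests to categorical secondary endpoints, and the Multiplicity paragraph in 7.3 commits to reporting all analyses. The times themselves are collected, including the time of expulsion at home (3.3, II.B). This stands too: the gap is in the list of endpoints and analyses, and data collection is complete.

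A reader might infer that a significant shorter stay could hide an induction about 7 h longer. The documents do not support that, for three reasons.
- The 7 h combines the design means with a full home period. Section 7.1 calls the same 4 h effect conservative, the cited savings imply about +1.4 h or −0.1 h, and section 1.1 reports no significant difference in total induction time in the cited outpatient-versus-inpatient Foley trial.
- Some women return early or never go home, and 4.4.2 keeps crossovers by intention to treat. If, as an illustration, 10% or 20% had no home hours, the average home time would be 9.9 or 8.8 h, and 7 h would become 5.9 or 4.8 h.
- A true 7 h shift would usually appear in the 24 h and 12 h counts.

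What the objection does not answer is that no estimate in hours is planned, and that shifts of 3 to 4 h are detected much less well on the counts.

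**Conclusion.** The point holds as a gap in the pre-specified analysis that costs little to close. For a moderate lengthening, the better of the two informative counts gives up about 23 percentage points of power at 4 h (80% against 57%) and 19 points at 3 h (56% against 37%), and no count yields a difference in hours. These sizes rest on normal times and on a control mean of 16 h and SD of 8 h borrowed from the hospital-hours assumption; the SD range above changes the levels, but the interval keeps the advantage.

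The finding does not touch the primary endpoint or the sample size, which reproduces. Nor does it say that outpatient ripening will lengthen induction: the documents' own figures span about −0.1 h to +7 h with 11 h at home.

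**What to change.** In section 3.3, III.J, add hours from initiation of cervical ripening to delivery as a continuous secondary endpoint. Keep the existing III.J starting point and define it identically in both groups as the earlier of the first Foley time (III.C) and the first pharmacologic ripening time (III.D), with delivery from III.I. State in advance which time applies if neither is recorded.

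Name the endpoint in 2.2 and 7.3. Analyse it by the same method as the primary endpoint, and report the mean difference with its 95% CI beside the primary result. Keep the III.J and III.K counts as supporting secondary results.

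The cost is a few lines in three sections, with no new data and no change in sample size. If total time does prove longer, the report will show it in hours next to the saving in hospital time.
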